Secondary outcomes consist of pain scores via NRS every four hours (if available) since PACU admission (pain score recorded to the closest time interval will be acceptable), the use of additional opioid medications (measured in morphine equivalents), length of hospital stay (number of postoperative days), reason for hospital length of stay > 1 night (i.e., social work/disposition, inadequate pain control, nausea/vomiting, other), complications during regional anesthesia block placement (inadvertent intravascular injection, inadvertent epidural or subarachnoid injection, local anesthetic systemic toxicity and pneumothorax) or during local infiltration analgesia injection (local anesthetic systemic toxicity), catheter-related complications (presence of site infection, hematoma, local anesthetic systemic toxicity), inadvertent catheter dislodgement, and a postoperative follow up at 12-16 weeks via telephone call or office visit evaluating multiple factors including a chronic pain assessment, health-related quality of life, and functional outcome specific to shoulder surgery.

Patients reporting a pain score via NRS > 3 at the 12-16 week postoperative period will be asked to complete the validated Leeds Assessment of Neuropathic Symptoms and Signs (LANSS) during the visit.^{26,27} The primary purpose of the LANSS scale is to assess nerve damage resulting in neuropathic pain.

Health-related quality of life will be assessed with the Medical Outcomes Study 12-Item Short Form (SF-12) questionnaire preoperatively and at the 12-16 week postoperative visit or telephone call. The SF-12 is a widely used, standardized and validated instrument.²⁸ Briefly, the SF-12 is a shorter version of the Medical Outcomes Study 36-Item Short Form (SF-36)²⁹, and scores 8 scales (physical functioning, role functioning-physical, bodily pain, general health, energy, social functioning, role functioning-emotional, and mental health), with higher scores indicating better health. SF-12 is commonly used as a general health-related quality of life measure in shoulder surgery.³⁰⁻³³

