3.3 Secondary Study Endpoints

1. Pain intensity (NRS) assessments prior to post-anesthesia care unit (PACU) discharge, every 4 hours beginning on arrival to patient room (to the closet time interval), and prior to hospital discharge or 12 pm on POD 1 (whichever comes first).
2. Opioid consumption in daily oral morphine equivalents (OME) – preoperative, intraoperative, PACU stay, and total beginning on arrival to patient room until patient discharge or up to POD 3 (whichever comes first).
3. Moderate to severe complications during regional anesthesia block placement (inadvertent intravascular injection⁺, inadvertent epidural or subarachnoid injection, local anesthetic systemic toxicity*, and pneumothorax) or during local infiltration analgesia injection (local anesthetic systemic toxicity).
 - a) ⁺*Inadvertent intravascular injection is suspected if a patient experiences sudden loss of consciousness, apnea, convulsions, hypotension, respiratory depression, nausea or dizziness, or stroke symptomology.*
 - b) ^{*}*Local anesthetic systemic toxicity is suspected if a patient has acute onset of central nervous system changes (tinnitus, metallic taste in mouth, perioral numbness) or cardiovascular changes (bradycardia, hypotension, EKG changes).*

4. Peripheral nerve block catheter-related complications including presence of site infection (tenderness to palpation, erythema, swelling, drainage of pus), hematoma, inadvertent catheter dislodgement, and local anesthetic systemic toxicity.
5. Duration of hospital stay (number of days), in addition to reason for hospital length of stay > 1 night (i.e., social work/disposition, inadequate pain control, nausea/vomiting, other)
6. Postoperative follow-up
 - a. Telephone encounter or office visit follow up 12 to 16 weeks postoperatively- NRS pain scores at rest and with movement of surgical extremity, postoperative neurologic changes (persistent numbness, paresthesia, or weakness of surgical extremity), and complications or adverse events will be noted.
7. Questionnaire Forms
 - a) SF-12
 - i. Collected preoperatively and at the 12-16 week postoperative visit or telephone call.
 - b) ASES
 - i. Collected preoperatively and 1-1.5 year postoperative visit or telephone call (data to be used in a follow-up study).
 - c) LANSS
 - i. Collected at 12-16 week follow-up visit to assess neuropathic pain in patients complaining of pain.

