6.1 Pre-Operative Plan

Following informed consent and randomization, study staff will record baseline patient demographics (including baseline NRS values for pain at rest, age, weight, gender, ASA physical status) from the electronic medical record and/or during the patient interview.

NRS pain scores at rest will be measured at the following time points: arrival to post-anesthesia care unit (PACU), prior to PACU discharge, every 4 hours beginning on arrival to patient room. Pain scores will be measured until hospital discharge from the time of the initial assessment in

the recovery room (PACU). All NRS pain scores will be recorded by registered nurses per standard protocol.

Regional Block – Both CISB and SISB:

Based on our current total joint regional anesthesia pathway (MC1156-462rev0115 and MC1156-1321rev1015), all patients will be provided (unless contraindicated and at the discretion of the attending anesthesiologist) a combination of oral analgesic medications preoperatively:

- 1) Tylenol 1 gram – at least 6 hours since last dose
- 2) Celecoxib 400 mg – for patients 18-64 years old and CrCl > 50 mL/min (if lab is available)
- 3)
 - a. Oxycodone (immediate release)
 - i. 5-10 mg once for patients 18-64 years old
- 4) Scopolamine Transdermal patch: 1.5mg - Apply to skin behind ear for 24 hours for high-risk patients (history of motion sickness or postoperative nausea vomiting). This is at the discretion of the anesthesiologist.

Local Infiltration Analgesia (LIA):

- 1) Tylenol 1 gram – at least 6 hours since last dose
- 2) Celecoxib 400 mg – for patients 18-64 years old and CrCl > 50 mL/min (if lab is available)
- 3)
 - a. Oxycodone (immediate release)
 - i. 5-10 mg once for patients 18-64 years old
- 4) Scopolamine Transdermal patch: 1.5mg - Apply to skin behind ear for 24 hours for high-risk patients (Hx: motion sickness or postoperative nausea vomiting). This is at the discretion of the anesthesiologist.

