7.2 Statistical Methods

Descriptive Statistics

Baseline characteristics will be summarized using mean and standard deviation for continuous variables that have a normal Gaussian distribution, and median and interquartile range for continuous variables with a non-normal distribution. Frequencies and percentages will be used to summarize categorical baseline characteristics. Baseline characteristics will be compared across groups using analysis of variance, or the Kruskal-Wallis test for continuous variables and the chi square test for categorical variables.

The primary aim of this study is to assess whether continuous interscalene nerve block provides superior analgesic benefit via OBAS compared to single injection interscalene blockade and local infiltration analgesia on POD 1 for primary total shoulder arthroplasty. In order to test this hypothesis, the will be compared across groups using ANOVA (or the Kruskal-Wallis test). Supplemental pairwise comparisons will be performed using two-tailed tests with $\alpha=0.017$ (Bonferroni adjusted) used to denote statistical significance. Similar analyses will be performed for secondary endpoints of pain and total additional opioid medications (moeq) until hospital discharge.

NRS pain scores measured at arrival to PACU, PACU discharge, and every 4 hours until time of hospital discharge following surgery will be analyzed using repeated measures ANOVA with pairwise treatment comparisons performed using linear contrasts.

Postoperative complications will be compared across groups using the chi-square test and hospital length of stay (number of postoperative days) will be compared across treatment groups using the Kruskal-Wallis test with supplemental pairwise comparisons performed using the rank sum test. Similar analyses will be performed for additional endpoints collected at the 12-16 week follow-up visit including NRS pain scores and SF-12 scales.

Our primary analysis will be performed based on the intention to treat. All calculated p-values will be two sided. For the overall analyses comparing across all 3 treatment groups simultaneously p-values less than 0.05 will be considered statistically significant. For supplemental pairwise treatment group comparisons p-values less than 0.017 (Bonferroni adjusted) will be considered statistically significant. The statistical analysis will be performed using SAS version 9.4 (SAS Institute Inc., Cary, North Carolina, United States).

Handling of Missing Data

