All Subjects enrolled according to the entry criteria will be eligible for evaluation, regardless of the sequence of treatment that ensues.

Management of dropouts and missing data will depend on their frequency and the nature of the outcome measure. Analysis of the distribution of prognostic factors between subjects with data and those without data will be reviewed for significance to assess selection bias. Adjustments for missing data will be performed only if deemed necessary and will be described

completely. An endpoint analysis (last observation carry forward), as described by Friedman⁴⁵ will be used for success rate assessments.

Outlier values will be evaluated for their validity; all data will be included unless judged to be invalid.

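### The repeated measures ANOVA planned for in-hospital NRS pain does not suit series with expected gaps and patient-specific end times, and no rule says how incomplete series enter it

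*Combined protocol and SAP*

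**What the plan says.** **Method.** Section 7.2 takes "NRS pain scores measured at arrival to PACU, PACU discharge, and every 4 hours until time of hospital discharge following surgery" and says they "will be analyzed using repeated measures ANOVA with pairwise treatment comparisons performed using linear contrasts". It names SAS 9.4 but no procedure, covariance structure or treatment of incomplete series. The same section also plans simple across-arm comparisons of pain, like those for OBAS, with pairwise tests at 0.017.

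**Collection.** Section 2 (Secondary Objective) describes "pain scores via NRS every four hours (if available) since PACU admission (pain score recorded to the closest time interval will be acceptable". Section 6.1 has ward nurses record the scores.

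**End of the series.** Section 6.1: "Pain scores will be measured until hospital discharge from the time of the initial assessment". Section 7.2 agrees, and the activity table in Section 6.3 marks pain scores for Days 2-5. Section 3.3 instead ends the series "prior to hospital discharge or 12 pm on POD 1 (whichever comes first".

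**Link between discharge and pain.** Section 3.3 collects the "reason for hospital length of stay > 1 night (i.e., social work/disposition, inadequate pain control, nausea/vomiting, other".

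**Missing data.** Section 7.2: "Management of dropouts and missing data will depend on their frequency and the nature of the outcome measure". Adjustment is made only where judged necessary. Last observation carried forward is confined to success rates, and NRS is not one.

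**Size.** Section 7.1 gives 39 effective patients per arm (43 randomised) and 80% power for 0.75 SD on NRS.

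**The concern.** Classical repeated measures ANOVA works on a rectangular table: every patient contributes a score at every time point. Its time and arm-by-time tests also assume sphericity, which is doubtful when readings 4 hours apart are likely to be more alike than readings a day apart. The plan expects data of another shape, with gaps inside the series and an end point that differs by patient.

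The noon cut-off in Section 3.3 reduces the second problem but does not remove it. Some patients may leave earlier. Because the end is a clock time, each 4 hours of later arrival on the ward also costs one scheduled reading.

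Two things are at stake. If incomplete patients are dropped, the analysis loses power that the sample size does not hold in reserve. If the length of a series depends on pain, the patients with long series are a selected group, and the arms may be selected differently. In an unblinded trial, how incomplete series are handled should be settled before the data are seen.

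**Working it through.** **1. The plan's own figure.** Inputs from Section 7.1: n = 39 per arm, d = 0.75 SD, alpha = 0.017 two-sided. That alpha is stated for OBAS and is assumed to carry over to NRS.

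Power = P(|T| > t[1 - alpha/2; 2n - 2]), where T is noncentral t with noncentrality d x sqrt(n/2).

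- n = 39: noncentrality 0.75 x sqrt(19.5) = 3.31, df 76, power **80.6%**. The stated 80% is reproduced.
- A simulated rank sum test on normal data (20,000 runs) gives 78.1%.
- Alpha 0.05 would give 90.5%, so the plan's 80% does imply 0.017.

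The figure needs all 39 patients per arm to contribute. The 10% attrition allowance in Section 7.1 names cancelled surgery and failed block as examples. It does not name missing readings.

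**2. Share of complete series.** Assumptions, because the documents give no rate: K = 8 readings (PACU arrival, PACU discharge, six 4-hourly), each present with probability p, independently. Complete share = p^K; patients left per arm = 39 x p^K.

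| p | p^8 | 39 x p^8 | n per arm | Noncentrality | Power, 0.75 SD at one reading |
|---|---|---|---|---|---|
| 0.90 | 0.430 | 16.8 | 17 | 2.19 | 38.3% |
| 0.95 | 0.663 | 25.9 | 26 | 2.70 | 59.5% |
| 0.97 | 0.784 | 30.6 | 31 | 2.95 | 69.0% |

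With 6 readings the shares are 0.531, 0.735 and 0.833, and power is about 48%, 65% and 71%. With 10 readings they are 0.349, 0.599 and 0.737, and power is about 29%, 54% and 65%.

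**3. Complete-case against all observed readings.** The table concerns one reading, whereas the planned contrasts may average over several. A simulation therefore compared the two approaches on the averaged contrast: two arms of 39, 8 readings, correlation 0.5, a constant 0.6 SD effect, alpha 0.017, 2,000 runs. The all-readings analysis weighted each patient by the known correlation, as a stand-in for a fitted mixed model.

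| Readings missing | Complete-case power | All observed readings |
|---|---|---|
| 0% | 87% | 87% |
| 2% | 80% | 86% |
| 5% | 67% | 87% |
| 10% | 40% | 85% |

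Both calculations take readings to be missing completely at random. They show loss of power and say nothing about bias. If gaps cluster in the same patients, more series stay complete and the complete-case loss is smaller than shown.

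**The case against.** The strongest reply is that the plan never says incomplete patients are removed. A reader might infer that anyone with one missing reading leaves the analysis. The documents do not support that as a statement of the plan. The label repeated measures ANOVA is also used for a long-format model with a patient effect, which keeps incomplete series. The missing-data text in Section 7.2 makes all enrolled patients eligible for evaluation, includes all valid data, and compares patients with and without data. Accepting the nearest recorded score will also fill some gaps. This stands, so the loss above is conditional on a complete-case analysis.

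Other points also stand:

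- Section 7.2 plans simple group comparisons of pain as well, and the 80% power figure matches a two-group test. The plan does not say which pain summary those comparisons use, or which analysis is the key secondary one.
- Sphericity does not affect the between-arm main effect. Its force is limited to the time and arm-by-time tests.
- A reader might infer that the analysis breaks a commitment to intention to treat. Sections 7.2 and 7.3 make that commitment for the primary analysis only.
- A reader might infer that the patients lost have less pain. The documents say nothing about missed readings and pain. They offer only the discharge link, and Section 3.3 lists disposition and nausea beside pain as reasons for a longer stay.

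The reply does not remove the mismatch. The same sentence in Section 7.2 permits analyses with very different samples and power, and nothing in the plan chooses between them.

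**Conclusion.** The point holds as a mismatch between the named method and the expected data, together with a missing rule. It does not hold as proof that patients will be deleted or that the result will be biased. It concerns the key secondary endpoint and leaves the primary OBAS analysis untouched.

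On a complete-case reading, with 8 readings independently present at 0.90 to 0.97, 17 to 31 of 39 patients per arm remain, and power at a single reading falls from 81% to between 38% and 69%. If all observed readings are used, the simulated loss is at most about 2 points. The size therefore rests on assumed missing rates and on an implementation that the plan leaves open. The effect of pain-related discharge on the comparison of arms cannot be quantified from the documents. The plan should be changed because the better method costs little.

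**What to change.** In Section 7.2, replace the repeated measures ANOVA with a linear mixed model for repeated measures on all observed readings:

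- **Terms:** arm, reading, arm-by-reading and baseline NRS at rest. Section 6.1 records baseline after randomisation, so state that it must precede the study intervention.
- **Covariance:** unstructured; if that does not converge, a prespecified time-dependent structure such as heterogeneous AR(1).
- **Inference:** Kenward-Roger degrees of freedom, and pairwise arm contrasts at 0.017 from this model. State which contrast is the key one (a named reading or the average over the window), and how it relates to the simple pain comparisons in the same section.
- **Window:** one common set of readings. Reconcile Section 3.3 (discharge or noon on POD 1) with Sections 6.1 and 7.2 (to discharge) and with the activity table. Without this, late readings may be too sparse for an unstructured covariance.
- **Sensitivity analysis:** for pain-related discharge, for example imputation with a range of shifts applied to post-discharge scores, plus a table of available readings by arm and time.

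Every randomised patient with at least one reading then stays in. The cost is a few sentences, with the same software and no new data. The downside is that the model assumes readings are missing at random, and it does not settle what pain after discharge means. The sensitivity analysis addresses the first; the second needs a stated definition.

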7.1 Sample Size Determination

The sample-size for this study was determined in order to provide statistical power of >90% to detect a difference of 3 units for the primary endpoint (OBAS on POD1). Based on a previous study, we hypothesize that the standard deviation of OBAS will be approximately 3 units.⁴⁴ Under this assumption, an effective sample-size of N=39 per group will provide statistical power of >90% to detect a difference between groups of 3 units using a two-sided, alpha=0.017 (multiple-comparison adjusted for 3 groups), non-parametric test. In addition, for the key secondary endpoint of pain (NRS), this sample-size will provide statistical power of 80% to detect a difference of 0.75 standard deviations (approximately 2.25 units on the NRS). In order to accommodate attrition of approximately 10% (due to canceled surgery, failed block, etc.) we propose a total sample-size of N=129 (43 patients per group).

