8.5 Stopping Rules

Adverse events and serious adverse events, as defined in Section 8.1 of IND protocol, will be monitored by the study team for patient safety. Known serious adverse events associated with interscalene nerve blocks (SISB and CISB groups) include inadvertent intravascular injection⁺, local anesthetic systemic toxicity (LAST)*, inadvertent epidural or subarachnoid injection, and pneumothorax. Additionally, patients will be monitored throughout the procedure utilizing standard ASA monitors, aspirating for heme or cerebral spinal fluid (CSF) prior to administration of local anesthetic solution in divided doses, frequent assessment of the patient's well-being via verbal communication, and having emergency medications and airway equipment readily available at all times. Performing this regional block is considered standard in our practice and these methods are already established procedures in the practice of perioperative pain control for a total shoulder arthroplasty.^{4,5}

Serious adverse event associated with local infiltration analgesia (LIA group) is local anesthetic systemic toxicity (LAST).

⁺ *Inadvertent intravascular injection is suspected if a patient experiences sudden loss of consciousness, apnea, convulsions, hypotension, respiratory depression, or stroke symptomology.*

^{*} *Local anesthetic systemic toxicity is suspected if a patient has acute onset of central nervous system changes (tinnitus, metallic taste in mouth, perioral numbness) or cardiovascular changes (bradycardia, hypotension, EKG changes).*

LAST is a known serious adverse event with any local anesthetic administration. Preventive measures include high degree of suspicion, vital sign monitoring (blood pressure, EKG, oxygen saturation), using an appropriate dose of local anesthetic, injecting local anesthetic in divided dose, aspirating prior to injection of medication looking for heme, consider using epinephrine in solution as a vascular marker, being prepared to treat a LAST event immediately (checklist, external defibrillator, resuscitate medications, emergency airway equipment), and having lipid emulsion therapy readily available (standard of care).⁴⁶ We acknowledge that despite the rarity of these serious adverse events, the potential still exists.

Study stopping criteria includes:

CISB and SISB groups:

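### The chi-square test for complications has no small-count fallback: with 43 per arm, a 3-0-0 split would be called significant (p=0.046) although the exact p is 0.106

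*Combined protocol and SAP*

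**What the plan says.** Section 7.2 gives one rule for complications: "Postoperative complications will be compared across groups using the chi-square test". The thresholds follow in the same section. "For the overall analyses comparing across all 3 treatment groups simultaneously p-values less than 0.05 will be considered statistically significant". For pairwise comparisons, "p-values less than 0.017 (Bonferroni adjusted) will be considered statistically significant". No exact test, rule for small expected counts or interval estimate is named for complications. For continuous outcomes such as the primary endpoint, by contrast, 7.2 does name a rank-based alternative.

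Section 7.1 sets the arm size: "we propose a total sample-size of N=129 (43 patients per group"), starting from 39 evaluable per arm. It states no event rate, expected count or power for complications.

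The events are listed in section 3.3. Item 3 covers complications of block placement or of the infiltration injection. Item 4 is a separate endpoint: "Peripheral nerve block catheter-related complications including presence of site infection", together with hematoma, dislodgement and systemic toxicity. Item 6 adds neurologic changes and complications noted at 12 to 16 weeks. Section 8.5, after naming intravascular injection, systemic toxicity, epidural or subarachnoid injection and pneumothorax, says the potential remains "despite the rarity of these serious adverse events".

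**The concern.** The chi-square p-value is a large-sample approximation, and it becomes unreliable when few events are expected per arm. With 43 patients per arm and events the protocol calls rare, such tables are likely for at least part of the list. A p-value that is too small could turn a handful of events in one arm into a declared difference.

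A second issue lies in the structure of the endpoints. Some listed events need a catheter, and only the continuous block arm has one by design. If those events went through the same three-arm test, a small p-value would restate the design and tell the reader nothing about relative safety.

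What is at stake is a secondary safety comparison. It still matters, because fewer block and catheter complications are part of the stated rationale for local infiltration (sections 1.1 and 1.3). The primary endpoint is not affected.

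**Working it through.** **Inputs.** 43 per arm, 129 in total (7.1); overall threshold 0.05 and pairwise threshold 0.017, two-sided (7.2). The plan has no figure for complications to reproduce. Its arm size does reproduce: 39 × 1.1 = 42.9, rounded up to 43. The event rate is not in the documents, so it is treated as an assumption with a range.

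**Step 1: expected events per arm = 43 × rate.**

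| Assumed rate | Expected events per arm |
|---|---|
| 1% | 0.43 |
| 2.3% (1/43) | 1.0 |
| 5% | 2.15 |
| 10% | 4.3 |
| 11.6% (5/43) | 5.0 |

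**Step 2: the 3-0-0 table.** Each arm has 1 expected event and 42 expected non-events.
- Chi-square = (2² + 1² + 1²)/1 + (2² + 1² + 1²)/42 = 6 + 0.143 = 6.143. With 2 degrees of freedom, p = exp(−6.143/2) = 0.0464.
- Exact p = 3 × C(43,3)/C(129,3) = 3 × 12,341/349,504 = 0.1059.
- With 39 per arm the values are 0.0460 and 0.1054, so attrition does not change the picture.

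**Step 3: other sparse tables, 43 per arm.**

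| Split | Chi-square p | Exact p | Ratio |
|---|---|---|---|
| 3-0-0 | 0.046 | 0.106 | 0.44 |
| 4-0-0 | 0.016 | 0.034 | 0.48 |
| 5-0-0 | 0.0055 | 0.0105 | 0.52 |
| 4-1-0 | 0.067 | 0.126 | 0.53 |
| 5-1-0 | 0.025 | 0.047 | 0.54 |
| 4-2-0 | 0.123 | 0.164 | 0.75 |

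The chi-square value is about half the exact one when events are concentrated in one arm. The gap narrows as they spread.

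**Step 4: how often the decision changes.** All three-arm tables with 43 per arm were enumerated.
- For totals of 1 to 9 events, 3-0-0 (in any arm) is the only split on which the tests disagree at 0.05. Given exactly 3 events and no true difference, chi-square rejects 10.6% of the time and the exact test never does. For 4 to 9 events the two rejection rates are identical. They part again at 10 events (6.6% against 4.6%).
- Averaged over the number of events, the chi-square false-positive rate is 0.3% at a 0.5% event rate, 1.2% at 1%, 3.4% at 2.3%, 3.8% at 5% and 4.6% at 10%. The exact test gives 0.01%, 0.1%, 1.0%, 3.0% and 4.2%.
- Pairwise, 3/43 against 0/43 gives chi-square p=0.078 and Fisher p=0.241. Neither passes 0.017.

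**Step 5: catheter-only events.** If these were tested across arms, the table would be k-0-0. Every k of 3 or more gives chi-square p<0.05. At an assumed rate of 5% in the catheter arm, the chance of 3 or more among 43 is 36%; at 10% it is 82%. An exact test does not cure this, since 4-0-0 still gives 0.034.

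**Step 6: what an interval adds.** For 0/43 the two-sided 95% Clopper-Pearson upper limit is 1 − 0.025^(1/43) = 8.2%. A p-value would not show that.

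**The case against.** The strongest counter-argument is that the planned test does control its error. Averaged over event totals, the chi-square false-positive rate stays below 5% at every rate checked, and the exact test is far more conservative at low rates, which is a cost in a safety comparison. The decision changes on only one small table. Under no true difference that table is uncommon: its probability is 10.6% times the chance of exactly 3 events, so 1.0% at a 1% event rate, 2.4% at 2.3% and 0.7% at 5%. All of this stands, and it limits the point to a minor one.

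Two stronger readings are tempting, and the documents support neither.

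- A reader might infer that about one event per arm is what the trial expects. No rate is given. The word rare in section 8.5 refers to the serious placement events, whereas 7.2 speaks of postoperative complications in general. Dislodgement, or neurologic symptoms at 12 to 16 weeks, could be commoner, and a pooled endpoint would have larger counts.
- A reader might infer that 7.2 sends catheter-only events through a three-arm test. It does not say so, and section 3.3 lists them as a separate endpoint. The wording leaves it open, so step 5 is conditional. Nor is a cross-arm display of block-placement events meaningless: avoiding a block-specific harm by choosing another technique is a legitimate contrast between strategies.

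Safety decisions during the trial also rest on the stopping thresholds in section 8.5, not on this p-value.

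**Conclusion.** The point holds as a minor gap in a secondary safety analysis. As written, 7.2 would declare a difference on a 3-0-0 split, where the exact p-value is 0.106, and it names no alternative for small counts. Expected counts are below 5 per arm for any rate under 11.6%; whether a given complication falls in that range is an assumption, plausible for the events called rare and unknown for the others. It would be wrong to say that the planned test has an inflated error rate overall: the 10.6% figure applies only given exactly three events. The catheter point depends on how 7.2 is read and is best settled by stating the intended analysis.

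**What to change.** In section 7.2:

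1. Use the Fisher-Freeman-Halton exact test for complications when any expected count is below 5, and chi-square otherwise.
2. Report each arm's complication rate with a 95% Clopper-Pearson interval.
3. Describe catheter-related complications (section 3.3, item 4) within the continuous block arm, with no three-arm test. Block-placement events may still be shown for all arms, as rates with intervals.
4. State which complications, if any, are pooled for testing.

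This takes a few sentences, with no new data and no change in sample size. The exact test is conservative, so a little power is lost on an endpoint the trial was not powered for.
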